9.1 General Conventions

Categorical variables will be summarized descriptively by frequency counts along with associated percentages. Continuous variables will be summarized descriptively using number of subjects, mean, standard deviation, minimum, median, and maximum. Analyses will be performed using SAS version 9.4 or later. Any final analyses that differ from what has been specified in this document will be identified within the final statistical output and documented within the clinical study report.

9.2 Disposition of Study Subjects

Subject disposition will be summarized using counts and percentages. The number and percentage of subjects completed and discontinued will be tabulated along with the specific reasons for discontinuation.

9.3 Demographic and Baseline Characteristics

Summary statistics of subject demographics (age, gender, race, ethnicity, weight, height, and BMI) will be presented. Similar summaries will also be provided for baseline and surgical characteristics including subject being of child bearing age, surgical procedure, procedure duration, TBS-related data, and other surgical and treatment-related data.

Medical history will be summarized by Medical Dictionary for Regulatory Activities (MedDRA) system organ class and preferred term. A listing will be presented for medical history. Surgical history and concomitant medications will be listed only.

9.4 Primary and Secondary Endpoint Analyses

9.4.1 Primary Endpoint Analyses

Descriptive summaries appropriate for continuous data will be provided overall and by pediatric groups (1 month [≥ 28 days from birth] to <1 year, and ≥ 1 year to ≤ 18 years) for the primary endpoint, absolute time to hemostasis. Primary endpoint data will also be summarized descriptively for Infants and Toddlers (28 days to 23 months), Children (2 to 11 years) and Adolescents (12 to <18 years).

A two-sided distribution-free 95% CI for median absolute time to hemostasis will be estimated for descriptive purposes only. The following example of SAS code can be used for this purpose:

```
proc univariate data=hemo CIPCTLDF;
var abstime;
run;
```

In addition, absolute time to hemostasis will be analyzed descriptively separately for subjects who achieved hemostasis with and without additional treatments being required.

9.4.2 Secondary Endpoint Analyses

All secondary endpoints, presented in Section 1, will be summarized descriptively using counts and percentages.

In addition, for success/failure secondary endpoints (4 and 10 minutes hemostasis endpoints), two-sided 95% CIs will be estimated for the proportion of success in EVARREST-treated subjects, using the Clopper-Pearson method, for descriptive purposes only.

9.4.3 Safety Analyses

All AEs will be summarized by number of subjects and associated percentage for relationship to the study product and procedure, seriousness, severity, action taken, and outcome. In addition, all AEs reported during the study will be coded to the Medical Dictionary for Regulatory Activities (MedDRA) version 19.0. All AEs will be summarized by MedDRA system organ class and preferred term by age group (Infants and Toddlers [28 days to 23 months], Children [2 to 11 years] and Adolescents [12 to <18 years]) and in total, using the number and percentage of subjects. Separate summaries will be provided for product-related and procedure-related AEs. Serious AEs, as well as non-serious AEs, will be summarized in a similar manner. Related events are those where the relationship is indicated as Related or Possibly related.

Laboratory values (including hemoglobin, hematocrit, and platelets) will be listed and summarized descriptively. Changes from baseline will also be summarized. Clinically significant changes will be reported as part of the AE listings.

Estimated intra-operative blood loss will be summarized as a continuous variable. Similarly, the volume of blood product transfused will be summarized as a continuous variable by type of product used.

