7.2. Procedures for Handling Biological Samples

7.2.1. Laboratory Tests

All laboratory investigations will be performed at the local hospital laboratory. The volume of blood to be taken will be determined according to the standard practices of each hospital. The normal reference ranges and laboratory accreditation certificates will be provided to the Sponsor.

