8.4.2. Methods of Analysis

Adverse events will be summarized descriptively, using Medical Dictionary for Regulatory Activities (MedDRA) terminology. Separate summaries will be provided for study product-related and procedure-related AEs. Serious AEs will be summarized in a similar manner.

Laboratory values (including coagulation parameters) will be reported in International System (SI) units. Values and changes from baseline will be listed and summarized. Clinically significant changes will be reported as part of the AE summary.

AEs (MedDRA terminology) will also be summarized into Infants and toddlers (28 days to 23 months), Children (2 to 11 years) and Adolescent (12 to <18 years).

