	8.3 Demographic and Baseline Characteristics	9
	8.4 Primary and Secondary Endpoint Analyses	9
	8.4.1 Primary Endpoint Analyses.....	9
	8.4.2 Secondary Endpoint Analyses.....	9
	8.4.3 Safety Analyses	10
	8.5 Plans for Interim Analysis	10
	8.6 Handling of Missing Data.....	10
	8.7 Subgroup Analysis	10

1 Study Design

The objective of this study is to evaluate the safety and hemostatic effectiveness of EVARREST Fibrin Sealant Patch (EVARREST) in controlling mild or moderate soft tissue and parenchymal bleeding during open hepatic, abdominal, pelvic, retroperitoneal, and thoracic (non-cardiac) surgery in pediatric patients.

This is an open-label, multicenter, single-arm study evaluating the safety and effectiveness of EVARREST in controlling mild or moderate bleeding in hepatic parenchyma or soft tissue for which standard methods of achieving hemostasis are ineffective or impractical during surgery in pediatric patients.

For this study, approximately 12 sites in US and UK will be utilized for consecutive screening and enrollment. Subjects will be considered as enrolled when the Informed Consent and Assent Form(s), as appropriate, is signed. Eligible subjects will be treated with EVARREST. Subjects will be followed post-operatively through hospital discharge and at 30 days (± 14 days) post-surgery.

At least thirty-five (35) pediatric subjects with an appropriate mild or moderate bleeding TBS will be enrolled in this study. The age of the subjects enrolled in the study will be from 1 month to <18 years. This will include a minimum of 4 subjects aged 1 month (≥ 28 days from birth) to <1 year.

The Target Bleeding Site (TBS) will be the only region evaluated for the primary endpoint and all secondary effectiveness endpoints. The TBS is defined as the first actively bleeding site identified during the soft tissue or hepatic dissection related to the primary operative procedure with challenging mild to moderate bleeding. This site will then be assessed for hemostatic effectiveness after product application as described below.

Once the TBS is identified, the surgeon will immediately apply EVARREST at the actively bleeding TBS. The size of the treatment article applied should be sufficient for coverage of the entire TBS and should overlap the bleeding source with a margin of 0.5-1 inch (1-2 cm).

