9.7 Subgroup Analysis

All subgroup analyses planned for this study are presented in Sections 8.4.1. and 8.4.3.

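### Laboratory values from children aged 28 days to under 18 years at about 12 local laboratories are summarised raw, with no age split or use of the supplied reference ranges, so no table counts children who moved out of range.

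*SAP*

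**What the plan says.** SAP 9.4.3 gives the whole laboratory analysis: "Laboratory values (including hemoglobin, hematocrit, and platelets) will be listed and summarized descriptively. Changes from baseline will also be summarized". It adds: "Clinically significant changes will be reported as part of the AE listings". SAP 9.1 fixes the statistics: "Continuous variables will be summarized descriptively using number of subjects, mean, standard deviation, minimum, median, and maximum".

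On where the values come from, protocol 7.2.1 states: "All laboratory investigations will be performed at the local hospital laboratory". It continues: "The normal reference ranges and laboratory accreditation certificates will be provided to the Sponsor". SAP Section 1 expects "approximately 12 sites in US and UK will be utilized for consecutive screening and enrollment" and an age range of 1 month to under 18 years, with at least 4 children under 1 year.

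Protocol 8.4.2 is slightly fuller than the SAP: "Laboratory values (including coagulation parameters) will be reported in International System (SI) units". It places clinically significant changes in the AE summary, where the SAP places them in the AE listings. Protocol 7.1.1 asks for one pre-operative CBC and coagulation panel, and 7.1.4 for a second before discharge.

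On subgroups, SAP 9.7 says: "All subgroup analyses planned for this study are presented in Sections 8.4.1. and 8.4.3". The section numbers evidently mean 9.4.1 and 9.4.3. In 9.4.3 the three age groups are applied to AEs only.

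**The concern.** Laboratory results are a listed secondary endpoint in the protocol and a safety endpoint in the SAP. A raw value means little without the range that applies to that child in that laboratory. SI units align the scale of measurement but not the ranges. A mean or median hemoglobin, platelet count or aPTT pooled over infants and adolescents from several laboratories therefore partly describes the mix of ages and laboratories.

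The question a safety reader would ask is how many children were in range before surgery and out of range at discharge. No planned output answers it, although the sponsor will hold reference ranges. PT, aPTT and INR are collected but not named in SAP 9.4.3. What is at stake is how readable the laboratory safety results are in a small descriptive pediatric study.

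**Working it through.** The plan states no figure on this point, and the 35 subjects rest on no formal calculation, so there is nothing to reproduce. As a check of the interval method, exact Clopper-Pearson limits for 16/20 and 19/20 are 56.3% to 94.3% and 75.1% to 99.9%. These match the earlier pediatric trial reported in the protocol Introduction.

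**Step 1: what the passages produce together.**

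| Element | Planned? | Where |
|---|---|---|
| Individual listing | Yes | SAP 9.4.3, protocol 8.4.2 |
| n, mean, SD, minimum, median, maximum of values and changes | Yes | SAP 9.4.3 with 9.1 |
| Clinically significant changes with the AEs | Yes, term undefined | SAP 9.4.3, protocol 8.4.2 |
| Age split for laboratory values | No | SAP 9.4.3 with 9.7 |
| Low/normal/high classification, flag or shift table | No | neither document |
| Reference ranges sent to the sponsor | Yes, no use stated | protocol 7.2.1 |

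Pooling over age is inferred from the absence of a laboratory subgroup and from SAP 9.7. It is not stated in words. The protocol sentence on summaries by pediatric group (8.3.2) sits under Effectiveness.

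**Step 2: what the change table would show.** The inputs are 35 subjects (documents) and an assumed aPTT prolongation of 20 s in k children, with zero change in the rest. The 20 s is an illustration only, because the documents give no laboratory distributions.

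- k = 1: mean = 1 × 20/35 = 0.6 s, median 0, maximum 20 s.
- k = 2: mean = 2 × 20/35 = 1.1 s, median 0, maximum 20 s, SD = √[(2 × (20 − 1.143)² + 33 × 1.143²)/34] = 4.7 s.

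The mean and median barely move. The maximum and SD do show that something large happened, but not in how many children, nor whether the values left their own ranges.

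**Step 3: the same in SD units.** Suppose k of 35 children change by 3 within-subject SDs and the rest average zero. The mean shift is 3k/35, and its standard error is √[1 + (k/35)(1 − k/35) × 9]/√35.

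- k = 1: shift 0.09, SE 0.19
- k = 2: shift 0.17, SE 0.21
- k = 3: shift 0.26, SE 0.22

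One or two marked changes sit within the noise of the mean.

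**Step 4: how far the pooled minimum of raw values helps.** Assume 4 infants whose normal centre is g SD lower than that of 31 older children, normal distributions, and one older child at −2.5 SD for age. That child is the pooled minimum with probability Φ(2.5)³⁰ × Φ(2.5 − g)⁴:

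- g = 0: 81%
- g = 1: 63%
- g = 2: 19%
- g = 3: under 1%

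The gap g is assumed. This concerns raw values only and does not test changes from baseline.

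**Step 5: what a shift table would add.** Newly out-of-range children would appear as counts with exact 95% limits:

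- 1/35 = 2.9% (0.1% to 14.9%)
- 2/35 = 5.7% (0.7% to 19.2%)
- 3/35 = 8.6% (1.8% to 23.1%)
- 4/35 = 11.4% (3.2% to 26.7%)

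**The case against.** A reader might infer that an abnormality in a few infants would be invisible in the planned output. The documents do not support that. SAP 9.1 requires SD, minimum and maximum, so in Step 2 the 20-second change appears as the maximum. Every value is listed, and with about 35 treated children and essentially two panels each, the listing can be read in full. Changes judged clinically significant are reported with the AEs, and AEs are tabulated by the three age groups.

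A reader might also take these tests to be the sole objective check on bleeding and clotting. They are not. Estimated blood loss and transfused volume by product are summarised, and bleeding-related and thrombotic AEs are separate endpoints followed to 30 days.

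Three further points stand. Change from baseline is within child, so much of the age and laboratory offset cancels if the same laboratory runs both samples. A single-arm surgical study isolates no product effect, so a shift table would also count the effects of surgery, blood loss and transfusion. And the SAP's mention of hemoglobin, hematocrit and platelets introduces examples, so coagulation is unnamed but not excluded.

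These arguments reduce the consequence but do not close the gap. The listing is not said to flag out-of-range values, and an unflagged value cannot be judged without the range for that age and laboratory. Minimum and maximum give extremes, not counts. The reporting of clinically significant changes has no stated criterion, and neither document says who decides.

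**Conclusion.** The point holds as a gap in presentation. Raw values and raw changes are summarised without an age split, the supplied reference ranges have no planned use, and no table counts children who moved out of their own range. No abnormal result is lost, because it remains in the listing and large changes reach the minimum or maximum. The weakness is that the pooled summaries are hard to interpret across ages and laboratories.

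The size cannot be estimated from the documents. The 20-second, 3-SD and age-gap figures are assumptions chosen to show the mechanism. The conclusion rests on reading SAP 9.4.3 and 9.7 together as meaning no laboratory age split. The change is worth making because it is cheap and needs no new sample or visit.

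**What to change.** In SAP 9.4.3:

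1. Classify each CBC, PT, aPTT and INR value as low, normal or high against the reporting laboratory's range for the child's age.
2. Flag out-of-range values in the listing.
3. Add a baseline-to-discharge shift table with the number and percent newly out of range, overall and by the three age groups already used for AEs. Cells will be sparse, since only 4 children under 1 year are guaranteed, so the overall table carries most of the information.
4. Name PT, aPTT and INR explicitly, in line with protocol 8.4.2.
5. Keep the raw value and change summaries as planned.

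The cost is SAP wording, one set of tables, and data entry. Protocol 7.2.1 does not say that the supplied ranges are age-specific, so they may have to be requested by age band and must be entered in the database. No blood draw, visit or clinical rule changes.

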7.1.2. Baseline Assessments (Within 24 Hours Prior to Procedure)

The following activities will be performed within 24 hours prior to the procedure. The timing of these activities may occur based on routine hospital practice and may overlap with some of the screening visit activities (see section 7.1.1).

- Review of inclusion / exclusion criteria to confirm subject pre-operative eligibility. In the event that a subject is no longer eligible, the reason for the screen failure will be documented on the source documentation and screening log.
- Documentation of all concomitant medications as stated in Section 6.3
- Documentation of any changes in medical history since the screening visit (if done on a separate visit from Baseline)
- Document subject weight and calculate maximum EVARREST units that could be used during the procedure
- Serum or urine pregnancy test (for female subjects of childbearing age)
- At least one CBC with differential, coagulation parameter testing and pregnancy test (if applicable) are needed pre-procedure. If pre-operative blood tests are repeated, only the test results closest to the date prior to surgery will be collected

The maximum size of EVARREST to be implanted is 6.9 square cm per kilogram of body weight. Where subject's body weight allows additional pads to be placed, a maximum of eight units (each unit size used is 2x4 inches (5.1 x 10.2 centimeters)), may be implanted (left in place at the bleeding site) per subject assigned to be treated with EVARREST.

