- Laboratory tests (including hemoglobin, hematocrit, platelets)
- Estimated intra-operative blood loss

- Number and volume of blood products transfused

2 Treatment Assignment

This is a single-arm study in which all subjects will have EVARREST applied at the actively bleeding TBS during the surgical procedure.

3 Randomization and Blinding Procedures

As this is a single-arm study, no randomization will occur, and no blinding procedures are required.

4 Interval Windows

Interval windows for the purpose of analysis in this study will not be defined outside of those for visit scheduling. The final visit occurs approximately 30 days after surgery. There will be a window of 14 days around the scheduling of the 30-day follow-up visit, and any information entered in the eCRFs at this visit will correspond to the associated visit. There will be no assigning of observations to time points outside of the visit to which they are recorded in the eCRFs.

5 Primary and Secondary Endpoints and Associated Hypotheses

Study endpoints are presented under the Study Design section. No hypotheses testing will be performed for this study.

6 Levels of Significance

No formal hypothesis testing will be performed for this study. A two-sided 95% distribution-free confidence interval (CI) for median absolute time to hemostasis will be estimated. In addition, for success/failure secondary endpoints (4 and 10 minutes hemostasis endpoints), two-sided 95% CIs will be estimated for the proportion of successes in EVARREST treated subjects, using the Clopper-Pearson method. All CIs will be estimated for descriptive purposes only.

7 Analysis Sets

The following four analysis sets are defined:

- All Enrolled Set (AES) consists of all subjects who provided informed consent or assent form for this study.
- Full analysis set (FAS or intent-to-treat set) consists of all enrolled and eligible subjects for whom TBS was identified. Subjects who do not complete the procedure after TBS identification will be included in the FAS analysis.
- Evaluable analysis set (or per-protocol [PP] set) consists of all FAS subjects who have no major protocol deviations affecting the primary endpoint and have data available for this endpoint.
- Safety analysis set will consist of all subjects who received treatment.

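### Blood loss and transfused volume are summarised without weight scaling or an age split, so these two summaries will largely reflect body size and respond little to heavy relative losses in infants

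*SAP*

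**What the plan says.** The SAP's study design section lists estimated intra-operative blood loss as a safety endpoint, and also "Number and volume of blood products transfused". SAP 9.4.3 specifies the analysis in two statements: "Estimated intra-operative blood loss will be summarized as a continuous variable", and "the volume of blood product transfused will be summarized as a continuous variable by type of product used". SAP 9.1 defines what a continuous summary contains: "Continuous variables will be summarized descriptively using number of subjects, mean, standard deviation, minimum, median, and maximum".

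The only age split in SAP 9.4.3 is for adverse events: "All AEs will be summarized by MedDRA system organ class and preferred term by age group". SAP 9.7 then closes the list: "All subgroup analyses planned for this study are presented in Sections 8.4.1. and 8.4.3". Those section numbers are one off; 9.4.1 (primary endpoint) and 9.4.3 (safety) are evidently meant. Protocol 8.4.1 and 8.4.2 follow the same pattern: both variables appear without scaling, and only adverse events are broken down by age.

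The population is wide: "The age of the subjects enrolled in the study will be from 1 month to <18 years". Weight is available. It is taken at screening (Protocol 7.1.1) and again at baseline (Protocol 7.1.2: "Document subject weight and calculate maximum EVARREST units that could be used during the procedure"), and SAP 9.3 summarises it as a demographic.

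**The concern.** A given volume of blood means something very different in a small infant and in a near-adult. A pooled mean, SD, minimum, median and maximum in mL over this age range is largely a description of how big the children were. A heavy loss for an infant can sit near the bottom of the distribution, while the maximum will usually come from one of the larger children whatever their relative loss.

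The protocol sets a minimum number of infants under 1 year and ties the limit on product area to body weight, so it already treats body size and the youngest children as important. The blood-loss and transfusion summaries, as specified, are poorly suited to showing a relative excess in that group.

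There is a separate completeness gap. The number of blood products is a listed endpoint, but SAP 9.4.3 specifies an analysis of volume only. SAP 9.4.2 provides counts and percentages for secondary endpoints, and the SAP classes this one as a safety endpoint.

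**Working it through.** The plan states no figure for blood loss or transfusion, so there is nothing to reproduce. The checks below show how strongly unscaled volumes depend on body size.

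**Inputs from the documents**
- Ages 28 days to under 18 years; at least 35 subjects, at least 4 of them under 1 year (SAP 1). 4/35 = 11.4%.
- Patch unit 5.1 × 10.2 cm; product limit 6.9 cm² per kg; cap of eight units (Protocol 7.1.2). These serve only to show the weight span that the protocol allows for.

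**Assumptions, not in the documents**
- Infant weight 4 to 10 kg, older children 10 to 60 kg, typical loss 10 mL/kg.

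**1. Weight span implied by the protocol's own figures**
- One unit: 5.1 × 10.2 = 52.02 cm²; 52.02 / 6.9 = 7.5 kg.
- Eight units: 8 × 52.02 = 416.2 cm²; 416.2 / 6.9 = 60.3 kg.

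The points at which one whole unit and eight units are reached differ 8-fold in weight. They are not the weights of any subject.

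**2. Same volume, different weight** (mL/kg = mL / weight)

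| Weight | 100 mL expressed per kg | Ratio to 60 kg |
|---|---|---|
| 4 kg | 25.0 | 15 |
| 5 kg | 20.0 | 12 |
| 8 kg | 12.5 | 7.5 |
| 60 kg | 1.7 | 1 |

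Conversely, a loss of 10 mL/kg is 50 mL at 5 kg and 600 mL at 60 kg.

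**3. Fixed example: 4 infants of 6 kg and 31 older children of 30 kg, all losing 10 mL/kg**
- Infants lose 60 mL each, older children 300 mL each.
- Mean = (4 × 60 + 31 × 300) / 35 = 9,540 / 35 = 273 mL; median 300, maximum 300.
- Triple every infant's loss, to 180 mL: mean = (4 × 180 + 31 × 300) / 35 = 10,020 / 35 = 286 mL; median 300, maximum 300.

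A threefold relative excess in all the infants moves the mean by 5% and leaves the median and maximum unchanged. The minimum rises from 60 to 180 mL, which no reader would take as a warning. In mL/kg the infants stand at 30 against 10.

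**4. Simulation with variation between subjects** (35 subjects, 4 of them infants; infant weights uniform 4 to 10 kg, older weights log-uniform 10 to 60 kg; lognormal loss with median 10 mL/kg; 4,000 replicates per setting)

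| CV of loss per kg | Variance of log mL explained by log weight, no infant excess | Rise in pooled mean, 3-fold infant excess | Largest value is an infant's: mL | Largest value is an infant's: mL/kg |
|---|---|---|---|---|
| 0.4 | 74% | 6.3% | 0.9% | 98% |
| 0.6 | 58% | 6.3% | 2.2% | 88% |
| 1.0 | 38% | 6.3% | 4.7% | 64% |

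An infant excess of 2-fold or 4-fold raises the pooled mean by about 3% or 9%. With a 3-fold excess the pooled median goes from about 221 mL to 240–245 mL, while the infant median per kg is about 31–35 against about 10 in older children. The model takes loss per kg as unrelated to weight, so it shows what follows if loss scales with size; it does not estimate what this trial will observe.

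**The case against.** **The SAP does not say raw mL for blood loss.** Correct. It gives neither unit nor scaling, and mL/kg is also a continuous variable. Volume is explicit only for transfusion. For blood loss the exact statement is that unit and scaling are unspecified, and that nothing in either document points to scaling.

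**An age split may exist.** Protocol 8.3.2 calls for descriptive analysis overall and in two groups, under 1 year and from 1 year up, and its first sentence could be read to cover every variable. But it stands under Effectiveness, and SAP 9.4.3 and 9.7 do not carry it to these endpoints. Even if applied, the older group would mix toddlers with adolescents: at 10 mL/kg, a 10 kg child loses 100 mL and a 60 kg child 600 mL.

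**Other safety output covers infants.** This stands in part. SAP 9.4.3 summarises haemoglobin and haematocrit with changes from baseline, and these are concentrations that do not grow with body size. Adverse events are split by age, and the protocol synopsis makes bleeding at the target site after 10 minutes an adverse event. A reader might infer that the safety analysis as a whole cannot reveal harm in infants; the documents do not support that. None of these outputs replaces total blood loss or transfusion, however.

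**Blood loss covers the whole operation, over mixed procedures.** Also true. Scaling would not turn it into a clean measure of product safety, and the documents give no threshold for a dangerous loss. Scaling makes it readable across ages, no more.

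**Nothing depends on it.** No hypothesis is tested, no decision rule uses these variables, and mL/kg could be derived later with the departure documented under SAP 9.1. That bears on priority, not on whether to make the change.

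**Conclusion.** The point holds for the two summaries in SAP 9.4.3. As specified, they pool an age range over which weight may differ by a factor of about 7.5 to 15 (infants of 8 to 4 kg against 60 kg), with no scaling and no age split. In the fixed example, tripling the loss of all 4 infants moves the pooled mean only from 273 to 286 mL.

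The direction follows from blood loss and transfusion growing with body size. The size rests on assumed weights and on the assumed spread of loss per kg. A reader might also infer that adolescents will dominate the means and SDs; the documents do not settle that, because they fix no number of adolescents and the only age quota is the minimum of 4 infants.

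The unanalysed number of blood products is a separate gap that needs no assumptions and lends no support to the scaling point. With a purely descriptive plan and partial cover from laboratory changes and age-split adverse events, this is a cheap improvement and not a threat to the trial's conclusions.

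**What to change.** In SAP 9.4.3:

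- State the unit for estimated blood loss. Keep the mL summaries of both variables; Protocol 8.4.1 names transfused volume as something to be summarised, so scaling should be added beside it and not replace it.
- Add summaries of both variables in mL/kg, using baseline weight, with median and range, overall and by the three age groups already used for adverse events, plus under 1 year (already a group in SAP 9.4.1). Keep transfusion split by product type. The under-1-year group is nested in the 28 days to 23 months group, so label it as such.
- Add a subject listing with age, weight, mL and mL/kg for both variables. With perhaps 4 infants, the listing will be more informative than summary statistics.
- Report how many subjects were transfused, with the percentage, and the number of products, so that the listed endpoint has a stated analysis.
- In SAP 9.7, correct the cross-references and include these age splits.

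Cost: one derived variable per endpoint, a few more table rows and one listing. No new data and no change to conduct. The drawback is very small age cells, which is why the listing matters and why the cells should be read descriptively.
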